# 3.2 Secondary endpoint(s)

There are no power considerations for secondary endpoints.

# 4 Change to protocol specified analyses

The following analyses are updated and changed from protocol amendment version 1 dated 20 Apr 2021.

1. Section 2.5.2 Statistical hypothesis, model, and method of analysis: The initial within subject correlation structure used for SANDE symptom score in MMRM is updated from "Unstructured" to "Toeplitz". This also applies to the supportive analysis for SANDE symptom score stated in 2.5.4 Supportive analyses.

# 5 Appendix

# 5.1 Imputation rules of missing dates

#### 5.1.1 AE date imputation

#### 5.1.1.1 Adverse event end date imputation

1. If the AE end date month is missing, the imputed end date should be set to the earliest of the (treatment follow up period date, 31DECYYYY, date of death).

2. If the AE end date day is missing, the imputed end date should be set to the earliest of the (treatment follow up period date, last day of the month, date of death).

3. If AE year is missing or AE is ongoing, the end date will not be imputed.

#### 5.1.1.2 Adverse event start date imputation

The following table explains the notation used in the logic matrix. Please note that **missing start dates** will not be imputed.

	Day	Month	Year
Partial Adverse Event Start Date	Not used	MON	YYYY
Treatment Start Date	Not used	TRTM	TRTY

The following matrix explains the logic behind the imputation.

	MON MISSING	MON < TRTM	MON = TRTM	MON > TRTM
YYYY	(1)	(1)	(1)	(1)
MISSING	No convention	No convention	No convention	No convention
YYYY < TRTY	( 2.a )	( 2.b )	( 2.b )	( 2.b )
	Before Treatment	Before Treatment	Before Treatment	Before Treatment
	Start	Start	Start	Start
YYYY = TRTY	( 4.a ) Uncertain	( 4.b ) Before Treatment Start	( 4.c ) Uncertain	( 4.c ) After Treatment Start
YYYY > TRTY	( 3.a )	( 3.b )	( 3.b )	( 3.b )
	After Treatment Start	After Treatment Start	After Treatment Start	After Treatment Start

Before imputing AE start date, find the AE start reference date.

- 1. If the (imputed) AE end date is complete and the (imputed) AE end date < treatment start date then AE start reference date = min (informed consent date, earliest visit date).
- 2. Else AE start reference date = treatment start date

Impute AE start date

- 1. If the AE start date year value is missing, the date uncertainty is too high to impute a rational date. Therefore, if the AE year value is missing, the imputed AE start date is set to NULL.
- 2. If the AE start date year value is less than the treatment start date year value, the AE started before treatment. Therefore:
  - a. If AE month is missing, the imputed AE start date is set to the mid-year point (01JulYYYY).
  - b. Else if AE month is not missing, the imputed AE start date is set to the mid-month point (15MONYYYY).
- 3. If the AE start date year value is greater than the treatment start date year value, the AE started after treatment. Therefore:
  - a. If the AE month is missing, the imputed AE start date is set to the year start point (01JanYYYY).
  - b. Else if the AE month is not missing, the imputed AE start date is set to the later of (month start point (01MONYYYY), AE start reference date + 1 day).
- 4. If the AE start date year value is equal to the treatment start date year value:
  - a. And the AE month is missing the imputed AE start date is set to the AE reference start date + 1 day.
  - b. Else if the AE month is less than the treatment start month, the imputed AE start date is set to the mid-month point (15MONYYYY).
  - c. Else if the AE month is equal to the treatment start date month or greater than the treatment start date month, the imputed AE start date is set to the later of (month start point (01MONYYYY), AE start reference date + 1 day).

If complete (imputed) AE end date is available and the imputed AE start date is greater than the (imputed) AE end date, then imputed AE start date should be set to the (imputed) AE end date.

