# 2.8.1 Adverse events (AEs)

In Part 1, AEs will be summarized for TEAE, pre-treatment AE and post-treatment AE separately.

- 1. Pre-treatment AEs are adverse events started between ICF signature and prior to the first administration of randomized study treatment.
- 2. Treatment emergent adverse events (TEAEs) are adverse events started after the first administration of randomized study treatment or events present prior to start of the randomized treatment but increased in severity based on preferred term.
- 3. Post-treatment AEs are adverse events started after the last administration of randomized study treatment to the end of the study.

For Part 1 and Part 2, the number (and percentage) of subjects with AEs will be summarized for ocular and non-ocular respectively, by treatment, in the following ways:

- primary system organ class and preferred term.
- primary system organ class, preferred term and maximum severity.
- Standardized MedDRA Query (SMQ) and preferred term.

Separate summaries for TEAEs will be provided for study medication related AEs, death, serious adverse events (SAE), other significant AEs leading to discontinuation.

For ESS1, the number (and percentage) of subjects with AEs will be summarized for ocular and non-ocular respectively, by dosing posology (TID and BID) in the following ways:

- primary system organ class and preferred term.
- primary system organ class, preferred term and maximum severity.
- Standardized MedDRA Query (SMQ) and preferred term.

A subject with multiple adverse events within a primary system organ class is only counted once towards the total of the primary system organ class. All these analyses will be based on the most updated MedDRA version available prior to the database lock.

All adverse events reporting will be included in the subject listings respectively.

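### Three of the SAP's rules for partial AE start dates have no lower bound at informed consent, so an event that began after consent can be dated before it

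*SAP*

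**What the plan says.** SAP 5.1.1.2 sorts partial start dates by how their year and month compare with treatment start. Three rules cover events that fall before treatment:

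- Rule 2a (earlier year, month unknown): "If AE month is missing, the imputed AE start date is set to the mid-year point (01JulYYYY").
- Rule 2b (earlier year, month known): "the imputed AE start date is set to the mid-month point (15MONYYYY").
- Rule 4b (same year, earlier month): "Else if the AE month is less than the treatment start month, the imputed AE start date is set to the mid-month point (15MONYYYY").

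The consent date appears only in a reference date computed beforehand. If the event ended before treatment start, "then AE start reference date = min (informed consent date, earliest visit date"); in every other case the reference date is treatment start. Rules 3b, 4a and 4c use it. Rules 3b and 4c share the form "the imputed AE start date is set to the later of (month start point (01MONYYYY), AE start reference date + 1 day"). Rules 2a, 2b and 4b do not use it.

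A closing rule applies when the imputed start is later than the end date: "then imputed AE start date should be set to the (imputed) AE end date".

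SAP 2.8.1 reports Part 1 events in three classes. The first is defined as follows: "Pre-treatment AEs are adverse events started between ICF signature and prior to the first administration of randomized study treatment". Protocol 10.1.1 counts an occurrence as an adverse event only after written consent, and sends conditions already present at consent to medical history.

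**The concern.** A correctly recorded adverse event cannot have begun before consent, yet three rules can give it such a date. Their fixed points take no account of when the subject consented, and the closing rule is no protection because it can only move a start earlier.

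An event dated before consent falls outside the literal definition of a pre-treatment event in SAP 2.8.1. It did not start after the last dose, so it is not post-treatment. It is treatment-emergent only if it later worsened. The SAP does not say where it should be counted. At stake are the completeness of the Part 1 pre-treatment summary and the presence of onset dates that contradict the protocol's own definition.

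**Working it through.** The documents give no figure on this point, so there is none to reproduce.

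**When the rules fail.** Rules 2b and 4b date an event before consent exactly when consent falls in the event's month and after the 15th. Rule 2a does so when consent falls in the event's year and after 1 July. Rules 2a and 2b need treatment to start in a later calendar year than the event; rule 4b does not.

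**Worked cases** (each true onset is after consent):

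| Rule | Consent | First randomized dose | Recorded start | Imputed start | Days before consent |
|---|---|---|---|---|---|
| 4b | 20 Mar 2021 | 3 Apr 2021 | Mar 2021 | 15 Mar 2021 | 20 − 15 = 5 |
| 2b | 20 Dec 2020 | 3 Jan 2021 | Dec 2020 | 15 Dec 2020 | 20 − 15 = 5 |
| 2a | 20 Dec 2020 | 3 Jan 2021 | 2020 | 1 Jul 2020 | 30 + 31 + 30 + 31 + 30 + 20 = 172 |

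A known end date before dosing leaves all three results unchanged.

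**How often, among events with only the day missing.** The interval G from consent to first randomized dose is not visible in the documents, so it is assumed. Take every consent date over 365 days and every onset day from consent to the day before dosing, all equally likely. That gives 365 × G pairs.

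Let k be the days left in the consent month, counting the consent day, and L the length of that month.

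- Dosing falls in a later month when k ≤ G, and then k onset days lie in the consent month.
- The imputed date precedes consent when the consent day is after the 15th, that is, when k ≤ L − 15.
- Each month therefore contributes the sum of k from 1 to min(G, L − 15). The upper limit L − 15 is 16 for a 31-day month, 15 for a 30-day month and 13 for a 28-day February.

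| G (days) | Pairs dated before consent | All pairs | Share |
|---|---|---|---|
| 1 | 12 × 1 = 12 | 365 | 3.3% |
| 7 | 12 × 28 = 336 | 2,555 | 13.2% |
| 14 | 11 × 105 + 91 = 1,246 | 5,110 | 24.4% |
| 28 | 7 × 136 + 4 × 120 + 91 = 1,523 | 10,220 | 14.9% |
| 42 | 1,523 | 15,330 | 9.9% |

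Direct enumeration of the SAP rules gives the same counts. The share falls at longer gaps because more onsets lie in a month after the consent month, where the 15th is safely later than consent. Among cases that reach rule 4b, the share before consent is 100% at 7 days, 98.8% at 14, 31.1% at 28 and 14.6% at 42.

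**Year-only records.** In the same enumeration, which crosses one year end, every case that reached rule 2a was dated before consent. Those cases are 1.1% of year-only pre-dose records at 7 days, 2.1% at 14, 4.0% at 28 and 5.9% at 42.

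**With a floor.** Taking the later of the rule's date and the consent date in 2a, 2b and 4b leaves no start before consent at any gap tested. The worked cases become 20 March 2021, 20 December 2020 and 20 December 2020.

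**The case against.** The best reply is that the SAP already shows what it intends. Its matrix marks the cells for 2a, 2b and 4b as preceding treatment start. An entry on the adverse event form is by protocol after consent, so a sensible programmer would put it in the pre-treatment class. SAP 2.4.2 says that medications are classified from recorded or imputed dates; the SAP makes no such statement for adverse events. This stands in part: omission follows only if classes are assigned from imputed dates and the consent bound is applied literally. Assigning events to classes is nonetheless the evident purpose of the rules, and the impossible date arises either way.

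The reply is also right that the reach is narrow. The affected dates lie before treatment with or without a floor, so the missing floor does not change treatment-emergent counts. SAP 2.8.2 covers all deaths during the study, and all events are listed. SAP 2.8.1 sets up the three classes for Part 1 only. The start of the ESS1 reporting period is blacked out, so no effect there can be shown.

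Frequency is uncertain too. Protocol Table 8-1 puts screening and randomization on the same day, and Part 1 visits about 14 days apart, so few partial dates may occur and a missing month should be rare. On the other side, SAP 2.1.1.2 counts Part 1 treatment from the first dose of the actually randomized treatment, protocol section 3 masks when vehicle is given, and protocol 8.1 requires consent before any washout. A real gap is therefore possible, but its length is not visible.

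**Conclusion.** The concern holds as a minor defect. Rules 2a, 2b and 4b can date an adverse event before consent, contrary to the protocol's definition. On a literal reading, the event could then be missing from the Part 1 pre-treatment summary unless it later worsens and counts as treatment-emergent. The number of affected records is unknown. The range of about 10% to 24% applies to pre-dose events lacking only the day, and rests on an assumed gap of 7 to 42 days with uniform consent dates and onsets; it is 3.3% at a one-day gap.

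Three stronger readings are tempting and are not supported:

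- **About half of subjects are affected, because about half consent after the 15th.** Rules 2b and 4b apply only when the event falls in an earlier month than the first randomized dose. The percentages above are shares of partial-date events, not of subjects.
- **The events are lost from the safety reporting.** Only one Part 1 table is at risk, and only conditionally.
- **Rules 3b and 4c already floor at consent.** The reference date is consent-based only when the event ended before treatment start. Under 3b the event year is after the treatment year, so for a consistent record the floor is treatment start.

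That enrolment crossed a year end is suggested only by the SAP version dates (September 2020 and June 2021, both before database lock). It matters for 2a and 2b, not for 4b.

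**What to change.** In rules 2a, 2b and 4b, set the imputed start to the later of the stated mid-point and the informed consent date, whenever the recorded month or year allows a start on or after consent. If the recorded month or year lies wholly before consent, query the record instead, since the condition may belong in medical history. Keep the closing end-date cap. It would also help to state in SAP 2.8.1 whether the three classes use imputed dates.

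The cost is one phrase in the SAP applied to three rules, and about one line of code. No new data are needed.

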#### 5.1.2 Concomitant medication date imputation

#### 5.1.2.1 Concomitant treatment end date imputation

- 1. If CM end day is missing and CM month/year are non-missing, then impute CM day as the minimum of treatment end date and the last day of the month.
- 2. If CM end month are missing and CM year is non-missing, then impute CM day as the minimum of treatment end date and the end of the year (31DECYYYY).
- 3. Only include if ongoing records will have an imputed CM end date. If CM day/month/year is missing, then use the treatment end date + 1 day as the imputed CM end date.
- 4. If imputed CM end date is less than the CM start date, use the CM start date as the imputed CM end date.

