#### 2.4.2 **Prior**, concomitant and post therapies

Prior medications are defined as drugs taken and stopped prior to the first administration of randomized study treatment (Section 2.1.1.2). Any medication given at least once between the day of the first administration of the study treatment and the EORT Visit will be a concomitant medication, including those that were started pre-baseline visit and continued into the treatment period. Post therapies are defined as drugs taken after EORT Visit, including those taken prior to EORT Visit and continued until the end of study. Prior, concomitant medication and post therapies will be identified based on recorded or imputed start and end dates of taking the medication.

Prior, concomitant medication or post therapies will be summarized by treatment group (separately for ocular and non-ocular medications/therapies), presented in alphabetical order by ATC classification codes and preferred term. The tables will be presented with overall number and percentage of subjects receiving at least one drug of a particular ATC code and at least one drug in a particular preferred term. Medications will be coded according to the WHO Drug Reference List dictionary.

In addition, all information will be listed including the reported name, laterality, and treatment start/end date, etc.

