#### 5.1.2.2 Concomitant treatment start date imputation

The following table explains the notation used in the logic matrix. Please note that **missing start dates** will not be imputed.

	Day	Month	Year
Partial CMD Start Date	Not used	MON	YYYY
Treatment Start Date	Not used	TRTM	TRTY

The following matrix explains the logic behind the imputation.

	MON MISSING	MON < TRTM	MON = TRTM	MON > TRTM
YYYY	(1)	(1)	(1)	(1)
MISSING	Uncertain	Uncertain	Uncertain	Uncertain
YYYY < TRTY	( 2.a )	( 2.b )	( 2.b )	( 2.b )
	Before Treatment Start	Before Treatment Start	Before Treatment Start	Before Treatment Start
YYYY = TRTY	( 4.a )	( 4.b )	( 4.a )	( 4.c )
	Uncertain	Before Treatment Start	Uncertain	After Treatment Start
YYYY > TRTY	( 3.a )	( 3.b )	( 3.b )	( 3.b )
	After Treatment Start	After Treatment Start	After Treatment Start	After Treatment Start

- 1. If the CM start date year value is missing, the imputed CM start date is set to one day prior to treatment start date.
- 2. If the CM start date year value is less than the treatment start date year value, the CM started before treatment. Therefore:
  - a. If the CM month is missing, the imputed CM start date is set to the mid-year point (01JulYYYY).
  - b. Else if the CM month is not missing, the imputed CM start date is set to the midmonth point (15MONYYYY).
- 3. If the CM start date year value is greater than the treatment start date year value, the CM started after treatment. Therefore:
  - a. If the CM month is missing, the imputed CM start date is set to the year start point (01JanYYYY).
  - b. Else if the CM month is not missing, the imputed CM start date is set to the month start point (01MONYYYY).
- 4. If the CM start date year value is equal to the treatment start date year value:
  - a. And the CM month is missing, or the CM month is equal to the treatment start date month, then the imputed CM start date is set to one day prior treatment start date.
  - b. Else if the CM month is less than the treatment start date month, the imputed CM start date is set to the mid-month point (15MONYYY).
  - c. Else if the CM month is greater than the treatment start date month, the imputed CM start date is set to the month start point (01MONYYYY).

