If complete (imputed) CM end date is available and the imputed CM start date is greater than the (imputed) CM end date, then imputed CM start date should be set to the (imputed) CM end date.

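### The conmed end-date rules cap a partial end date at treatment end even when the recorded month is later, so drugs continued past treatment drop out of the post-therapy summary

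*SAP*

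**What the plan says.** SAP 5.1.2.1 gives four rules for concomitant medication end dates.

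- Rule 1 (day missing): "impute CM day as the minimum of treatment end date and the last day of the month".
- Rule 2 (month missing, year known): the earlier of treatment end and 31 December of the recorded year.
- Rule 3 (nothing recorded): "If CM day/month/year is missing, then use the treatment end date + 1 day as the imputed CM end date".
- Rule 4: "If imputed CM end date is less than the CM start date, use the CM start date as the imputed CM end date".

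SAP 5.1.2.2 imputes start dates. If the start month is known and falls later in the same year than the treatment start month, the start becomes the first of that month. A closing rule covers an imputed start that lands after the end date: "then imputed CM start date should be set to the (imputed) CM end date".

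SAP 2.4.2 calls a drug concomitant if it was given at least once from first dose to the EORT Visit, and a post therapy if it was taken after that visit. It adds that prior, concomitant and "post therapies will be identified based on recorded or imputed start and end dates of taking the medication".

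**The concern.** Filling in a missing day should give a date inside the recorded month. Rules 1 and 2 do not ensure this. When the recorded month or year is after treatment end, the minimum is always treatment end, a date that the record rules out.

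The post-therapy table is meant to describe what subjects took once treatment stopped, and this rule removes drugs known to have been taken then. Protocol Table 8-2 schedules concomitant medications at Days 126, 154, 182 and 210 of Part 2, after treatment ends at Day 84. The SAP also treats adverse events differently: SAP 5.1.1.1 caps their partial end dates at the treatment follow-up date, the month or year end, or death. An event and the drug given for it, both recorded as ending in the same later month, can therefore get end dates in different months.

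Separately, rule 4 and the closing rule of SAP 5.1.2.2 resolve the same conflict in opposite directions. Two programmers could both follow the SAP and produce different concomitant and post-therapy tables and, for a prohibited drug, a different by-arm table under SAP 2.4.2.2.

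**Working it through.** The plan states no figure to reproduce. The check applies its rules to test records.

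**Inputs.** The rules are those of SAP 5.1.2.1, 5.1.2.2 and 2.4.2. The dates are assumed for illustration on the Part 2 schedule: treatment start 08Mar2021, treatment end 30May2021 (start + 83 days, Day 84), and the EORT Visit on the same day as treatment end.

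**Classification.** Concomitant if start ≤ EORT Visit and end ≥ treatment start. Post therapy if end > EORT Visit.

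**Step 1, the cap.** For an end recorded as --Jul2021, rule 1 gives min(30May2021, 31Jul2021) = 30May2021. That is 32 days before 1 July and 62 days before 31 July.

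**Step 2, the full rules, in both possible orders.**

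| Record | Start recorded | End recorded | Rule 4 first | Closing rule of 5.1.2.2 first |
|---|---|---|---|---|
| 1. Begun during treatment | 20Apr2021 | --Jul2021 | 20Apr to 30May: concomitant only | same |
| 2. Begun before treatment | 01May2019 | --Jul2021 | 01May2019 to 30May2021: concomitant only | same |
| 3. Begun during treatment | 20Apr2021 | nothing | 20Apr to 31May: concomitant and post | same |
| 4. Used only after treatment | 10Jun2021 | --Jul2021 | 10Jun to 10Jun: post only | same |
| 5. Used only after treatment | --Jun2021 | --Jul2021 | 01Jun to 01Jun: post only | 30May to 30May: concomitant only |
| 6. Used only after treatment | --Jun2021 | 2021 only | 01Jun to 01Jun: post only | 30May to 30May: concomitant only |

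Records 1 and 2 are the clear failure. The start precedes the imputed end, so neither conflict rule acts and order is irrelevant. A drug recorded as used into July is not a post therapy, although record 3, with less information, is. Record 4 is rescued by rule 4, with its duration cut to one day. Records 5 and 6 depend on an order that the SAP does not state.

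**Step 3, with the cap lifted when the recorded month is after the treatment-end month.** Records 1 and 2 end on 31Jul2021 and are both concomitant and post. Record 4 becomes 10Jun to 31Jul. Record 5 becomes 01Jun to 31Jul and is post under either order. Record 6 does not change, because its recorded year is the same as that of treatment end. The order must therefore be settled as well.

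**The case against.** The strongest reply is that rule 4 already protects the drugs that matter most. A reader might infer that drugs used only after treatment are in general dated into the treatment period. The documents do not support that: with a complete start date such a drug stays a post therapy (record 4). It is pulled back only if its start is also partial and, for a start in a known later month, only if the closing rule of SAP 5.1.2.2 runs before rule 4. A start with only the year known, in the treatment-start year, is a separate matter, because SAP 5.1.2.2 itself sets it to the day before treatment start.

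Nor is every end date recorded in a later month imputed wrongly. With start 10Jul2021 and end --Jul2021, rule 4 gives 10Jul2021, which lies inside the recorded month.

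The contrast with rule 3 is also weaker than it looks. Its wording refers to ongoing records, for which a date after treatment is reasonable. Treatment end + 1 day counts as post only if the EORT Visit coincides with treatment end, and the visible SAP does not define that visit.

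A reader might also take the share of Part 2 days after treatment, (210 − 84)/210 = 60%, as the size of the problem. It measures calendar time at risk, not the number of affected records, and Part 2 is exploratory and starts only if Part 1 succeeds.

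All of this stands. It leaves records 1 and 2 untouched, along with the missing order for records 5 and 6.

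**Conclusion.** The end-date rule is wrong as written for one definite group: drugs begun before or during treatment whose end day is missing and whose recorded end month is after the treatment-end month. Their imputed end contradicts the record and they leave the post-therapy summary under either rule order. This holds whenever the EORT Visit is on or after treatment end. It also reads the post-therapy definition as covering any drug taken after that visit, not only one continued to end of study. For drugs used only after treatment with a partial start in a known later month, the class is undetermined.

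The point is minor. It touches descriptive medication tables, and the number of affected records cannot be estimated because the frequency of partial dates is not given. A reader might infer an effect on the primary analysis, but the documents do not support one. SAP Table 2-4 sets data after treatment discontinuation to missing, and SAP 2.4.2 ties the imputed dates to medication classes only.

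**What to change.** 1. In SAP 5.1.2.1 rules 1 and 2, apply the treatment-end cap only when the recorded end month (or year, if the month is missing) is not after that of treatment end. Otherwise impute the last day of the recorded month (or 31 December), capped at the subject's last contact or follow-up date or death. The cap should not be the visit labelled EOS. Protocol Table 8-2 puts that at Day 126, with safety follow-up to Day 210. On the dates above Day 126 is 11Jul2021 (start + 125 days), so an end recorded as --Aug2021 would again be cut to a date outside its month.

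2. Replace rule 4 and the closing rule of SAP 5.1.2.2 with one conflict rule: move the imputed date whose recorded information is less complete, and never move a date outside its recorded month or year. Record 6 then resolves to 01Jun2021 and is post. Always moving the end up to the start would not do. With treatment start 08Mar2021, a start recorded as 2021 only is imputed to 07Mar2021, and an end recorded as --Jan2021 to 31Jan2021. Moving the end would push it out of January, whereas the single rule moves the start to 31Jan2021, as the closing rule does now.

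The cost is a few sentences in the SAP appendix and a small program change. No new data are needed.
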